## 6 STUDY PERIODS, TREATMENT REGIMENS AND POPULATIONS FOR ANALYSES

### 6.1 Study Periods

Study periods for efficacy and safety analyses are defined as follows:

- **Pre-treatment period** begins at the first visit until initiation of study therapy.
- **On-treatment period** begins after the first day of study therapy and ends at the last dose of study therapy plus 5 days.
- **ETV treatment period** begins after the first day of active ETV and ends at the last dose of active ETV plus 5 days.
- **Off-treatment follow-up period** begins on the last dose of study therapy plus 6 days and ends at the start of alternative anti-HBV therapy minus 1 day.
- **Long-term follow-up period** begins on the last dose of study therapy plus 6 days until the end of the study.
- **Alternative ETV follow-up period** begins on the later of the last dose of study therapy plus 6 days and the start of alternative ETV therapy, until the end of the study.

Note that rescue open-label ETV is considered alternative anti-HBV therapy. See [Section 8.9](#) for additional conventions.

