## 7 STATISTICAL ANALYSES

### 7.1 General Methods

All analyses (efficacy, safety and PK) are presented by treatment regimen, ie, ETV vs PBO, based on the appropriate cohort and dataset defined in the earlier section. For Week 48 analysis, all the endpoints are to be cut off through Week 48, unless specified otherwise.

The PK analyses are described in [Section 7.7](#). The methods described below are used to analyze safety and efficacy data.

Categorical variables are summarized either with counts and percents or with proportions (number with event divided by number evaluable) and percents, depending on the endpoint.

Continuous variables are summarized with univariate statistics (eg, n, mean, median, standard deviation, standard error, quartiles, minimum, and maximum).

Longitudinal analyses of efficacy and safety parameters use pre-defined visit week windows (see [Section 8.4](#)). Windows around planned measurement times are constructed based on the

midpoint between planned measurement visits unless specified otherwise. Data are summarized at each scheduled visit through the analysis week.

Analyses of HBV DNA use values only from the central laboratory from the Roche COBAS® TaqMan HBV Test with limit of quantitation (LOQ) of 29 IU/mL and limit of detection (LLD) of 10 IU/mL.

Analyses of laboratory tests and serology use values from the central or local laboratory. Laboratory parameters are summarized using US standard values and units. Refer to [Section 8.11](#) for conversion of select laboratory test values from the Abbott Architect system to the Roche Diagnostics Hitachi Modular system.

Formats of tables, listings and graphs are described in the Data Presentation Plan (DPP).

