For PBO-treated subjects who receive open-label ETV, baseline is used during blinded dosing, while ETV baseline is used during open-label ETV dosing.

Laboratory abnormalities by toxicity grade (Grade 1 - 4; Grade 3 - 4) are also summarized by treatment regimen and EOD status (all, normal, abnormal) for the first 2 follow-up cohorts: (1) off-treatment follow-up for off-treatment follow-up subjects in the Post-Year 1 Safety Cohort; (2) long-term follow-up for long-term follow-up subjects in the Post-Year 1 Safety Cohort.

Laboratory abnormalities by toxicity grade (Grade 1 - 4; Grade 3 - 4) are also summarized by treatment regimen during alternative ETV follow-up for alternative ETV follow-up subjects in the Post-Year 1 Safety Cohort.

Emergent laboratory abnormalities by toxicity grade (increased to Grades 1, 2, 3 and 4) are also summarized analogously by treatment regimen and EOD status for the first 2 follow-up cohorts. Emergent abnormalities are those with a higher toxicity grade than the EOD toxicity grade.

Select laboratory elevations and abnormalities are summarized relative to the EOD value for the 3 follow-up cohorts. In addition, elevations of liver function tests (including ALT flares, defined as ALT > 2 x reference and > 10 x ULN) during the follow-up periods are summarized using the reference value (REF) (ie, minimum of the baseline and EOD values) for the 3 follow-up cohorts. Note that for PBO-treated subjects who receive open-label ETV, reference is the minimum of the ETV baseline and EOD values.

ALT multiples of ULN and HBV DNA values are plotted over time for each subject who had an ALT flare on study. The duration of an ALT flare is measured from the first ALT measurement meeting the ALT flare criteria to resolution, defined as (1) the first ALT  $\leq$  baseline or  $\leq 5$  x ULN on treatment, or (2) the first ALT  $\leq$  reference or  $\leq 5$  x ULN during follow-up. If (1) and (2) are not met, an ALT flare is considered unresolved, and the last ALT measurement is used to estimate duration.

The time to and duration of ALT flares (weeks) during off-treatment follow-up are summarized for off-treatment follow-up subjects in the Post-Year 1 Safety Cohort (limited to ETV, PBO OL, and All ETV). Analyses are based on the first ALT flare during off-treatment follow-up.

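### SAP 7.6.6.1 enters unresolved off-treatment ALT flares as complete durations up to the last ALT, with no censoring and no stated window for that last ALT

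*SAP*

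**What the plan says.** SAP 7.6.6.1 gives the definition: "The duration of an ALT flare is measured from the first ALT measurement meeting the ALT flare criteria to resolution". Resolution during follow-up is the first ALT at or below the reference value or at or below 5 x ULN. A flare that does not get there is labelled unresolved, and "the last ALT measurement is used to estimate duration".

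The planned summary follows: "The time to and duration of ALT flares (weeks) during off-treatment follow-up are summarized", for off-treatment follow-up subjects in the ETV, PBO OL and All ETV groups. "Analyses are based on the first ALT flare during off-treatment follow-up". No method specific to these durations is named, so SAP 7.1 applies: "Continuous variables are summarized with univariate statistics".

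Two other sections bear on this. Under SAP 6.1 the off-treatment period "ends at the start of alternative anti-HBV therapy minus 1 day", and the same section adds: "Note that rescue open-label ETV is considered alternative anti-HBV therapy". SAP 8.9 dates alternative therapy from the earlier of rescue ETV and any concomitant anti-HBV medication.

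**The concern.** The duration of an unresolved flare is right-censored: it lasted at least until the last ALT, and how much longer is unknown. Pooling that value with completed durations in a mean or median pulls the summary down. SAP 7.4.1 treats the same kind of data differently, describing time on study therapy by Kaplan-Meier with censoring.

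The period definition could make this worse. If ALT values count only up to the day before anti-HBV therapy, a flare treated soon after detection may have no second ALT in the window, and its recorded duration is then 0 weeks.

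At stake is the description of how long post-treatment exacerbations last. Protocol 1.5 names exacerbation after treatment as a known risk, and SAP 9 makes off-treatment safety part of the minimum content of the final analysis.

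**Working it through.** The documents state no flare count, unresolved share, treated share or mean duration, so there is no figure of the plan's own to reproduce. The check is a bound, a formula and an illustration on assumed inputs.

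**1. The bound.** Let D be the time from the first flare ALT to the first ALT meeting the resolution criteria on the visit schedule, and C the time from the first flare ALT to the last ALT available. The SAP value is D if D ≤ C, and C otherwise, that is min(D, C). This never exceeds D and is smaller for every unresolved flare. It is 0 when the flare ALT is itself the last ALT.

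**2. A small example.** Take four resolved flares of 6, 8, 12 and 14 weeks and two unresolved at 1 and 2 weeks. The SAP rule gives a mean of 43/6 = 7.2 weeks and a median of 7. With the two unresolved flares censored, four remain at risk at week 6. Survival is 3/4 after week 6 and 3/4 x 2/3 = 1/2 after week 8, so the Kaplan-Meier median is 8 weeks.

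**3. A formula.** Assume an exponential resolution rate L and an independent censoring rate M. The mean of the minimum is 1/(L + M) = (1/L) x L/(L + M) = true mean x (1 - share unresolved). For an assumed true mean of 12 weeks:

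- 20% unresolved: 12 x 0.8 = 9.6 weeks
- 40% unresolved: 12 x 0.6 = 7.2 weeks
- 60% unresolved: 12 x 0.4 = 4.8 weeks

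**4. Simulation.** All inputs are assumed: exponential duration from detection with mean 16 weeks, remaining follow-up uniform on 0 to 120 weeks, and therapy in 0%, 25% or 50% of flares, starting 0.3 to 2 weeks after detection and independent of duration. The window closes at therapy, which is the truncating reading. With ALT every 2 weeks:

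| Share treated | Unresolved | Mean, complete follow-up on same schedule | Mean, SAP rule | Median, complete | Median, SAP rule | Median, Kaplan-Meier |
|---|---|---|---|---|---|---|
| 0% | 14% | 16.9 | 14.6 | 12 | 10 | 12 |
| 25% | 36% | 17.1 | 11.0 | 12 | 6 | 12 |
| 50% | 57% | 17.0 | 7.2 | 12 | 0 | 12 |

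The means agree with step 3: 16.9 x 0.86 = 14.5 and 17.1 x 0.64 = 10.9. Without truncation by therapy the loss is modest; most of the effect in this table comes from the truncating reading. Treated flares contribute 0 weeks here because the assumed start of therapy precedes the next ALT. With weekly ALT they contribute 0.6 weeks on average.

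**5. The opposite error.** Resolution is dated to the first qualifying ALT. Protocol 4.1 sets follow-up visits at Weeks 6 and 12 and then every 12 weeks. In the same simulation with ALT every 12 weeks, complete follow-up gives a mean of 22.7 weeks against a true 16. The SAP rule gives 18.4 with no therapy, above the truth, and 13.8 with 25% treated, below it. The pooled summary can therefore err in either direction against true duration. Against complete follow-up on the same schedule, no recorded duration can be too long.

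**The case against.** The strongest reply is that truncation at therapy is an inference. SAP 7.6.6.1 frames resolution as occurring during follow-up, without saying which follow-up period, and the same section uses follow-up periods for all three follow-up cohorts. SAP 6.1 runs long-term follow-up to the end of the study, through any rescue. The restriction to off-treatment follow-up may only select which flare is analysed; on that reading treated flares are not cut off. This stands as a real ambiguity. The wording of the summary, duration during off-treatment follow-up, leans towards truncation but does not settle it. If later ALTs are used, the durations include time on therapy.

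A reader might also infer that the plan makes the worst flares look briefest. The documents do not establish this. The period closes at any anti-HBV therapy, which Protocol 4.1.1 leaves to the treating clinician, so cut-off is not tied to rescue-level severity. Protocol 4.1.2 recommends additional testing for extreme elevations, which could supply more ALTs before therapy. Nor are unresolved flares treated as resolved: the SAP labels them correctly, and only their durations enter as complete values.

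Per-subject plots of ALT and HBV DNA are planned for every subject with a flare, and table formats sit in a Data Presentation Plan that is not among the documents. Both may show which flares were unresolved. Neither changes the stated duration rule.

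**Conclusion.** The point holds in limited form. The stated rule pools lower bounds with completed durations and understates duration relative to complete follow-up on the same visit schedule. That needs only one unresolved flare and no distributional assumption. The net error against true duration is uncertain, because sparse visits lengthen resolved durations.

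Early cut-off of treated flares is conditional on the last ALT being confined to off-treatment follow-up, which the SAP leaves open. The size cannot be derived from the documents; the figures above rest on assumed durations, visit intervals and treated shares, and on censoring independent of duration. That last assumption is doubtful when therapy is started because of the flare.

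No test, significance level, sample size or efficacy result is affected. It is a minor improvement to a descriptive safety summary.

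**What to change.** In SAP 7.6.6.1:

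- State which study period supplies the ALT values used for resolution and for the last ALT.
- Report the numbers of first off-treatment flares resolved, unresolved at last ALT, and ended by the start of anti-HBV therapy (rescue ETV or other).
- Replace the univariate duration summary with a Kaplan-Meier estimate of time to resolution, censoring unresolved flares at the last ALT.
- Because censoring by therapy is likely to be informative, do not rely on Kaplan-Meier alone. Its good performance in the simulation depends on therapy being independent of duration. Add the cumulative incidence of resolution with start of anti-HBV therapy as a competing event, or follow each flare through long-term follow-up with treated flares flagged, or do both. The second option measures duration including time on therapy, and the table should say so.

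The cost is a short SAP amendment, a small table and slightly more analysis. Chemistry is already scheduled at every long-term follow-up visit (Protocol Table 6.1) and therapy start dates are already derived (SAP 8.9), so no new data are needed.

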#### **7.6.6.2 Laboratory Tests over Time**

Laboratory test values are summarized by treatment regimen at baseline and each scheduled visit (see [Section 8.4](#)) for the following cohorts:

- On treatment through Week 48 for treated subjects
- On treatment through Week 96 for the Year 2 Safety Cohort
- On ETV treatment for the All ETV Safety Cohort

Values are also summarized by treatment regimen at EOD and each scheduled visit during (1) off-treatment follow-up for off-treatment follow-up subjects in the Post-Year 1 Safety Cohort, and (2) long-term follow-up for long-term follow-up subjects in the Post-Year 1 Safety Cohort.

Laboratory tests include:

- Hemoglobin
- Platelets
- INR
- WBC
- ALT
- Total bilirubin
- Albumin
- Lipase (colorimetric assay only)
- Creatinine

### **7.6.7 Growth/Development Assessment**

Growth assessment values and changes from baseline are summarized by treatment regimen at baseline and each scheduled visit (see [Section 8.4](#)) for the following cohorts:

- For treated subjects across the on-treatment and long-term follow-up periods combined
- For the Year 2 Safety Cohort across the on-treatment and long-term follow-up periods combined
- For the All ETV Safety Cohort across the ETV treatment and long-term follow-up periods combined

Growth assessment parameters include HAZ, HAP, WAZ, WAP, BMIAZ, and BMIAP. These parameters are derived using 2000 CDC growth charts.

Longitudinal plots display mean growth changes from baseline in growth assessment (HAZ, HAP, WAZ, WAP, BMIAZ, BMIAP) versus visit week by treatment regimen with error bars representing  $\pm 1$  SE of the reported statistic for treated subjects across the on-treatment and long term follow-up periods combined.

Tanner stage is a development assessment parameter that is summarized analogously by age randomization strata for each staging category (pubic hair, breast/genitals) and treatment regimen (see [Section 7.6.8](#)). Stages I - V are assessed as integers 1 - 5, respectively.

### **7.6.8 Results by Subgroups**

The following key safety endpoints are summarized by subgroups of age randomization strata, geographic region, HBV genotype and route of transmission (see [Section 7.5.1](#)) on blinded therapy through Week 48 for treated subjects, unless specified otherwise:

- SAEs
- AEs leading to discontinuation of study therapy
- Events of HBV disease progression (on-treatment and long-term follow-up periods combined)
- AEs by intensity (All Grades; Grade 2 - 4 related; Grade 3 - 4)
- Laboratory abnormalities by toxicity grade (Grade 1 - 4; Grade 3 - 4)
- Select laboratory elevations and abnormalities
- Growth/development assessment values and changes from baseline over time (on-treatment and long-term follow-up periods combined). Tanner stage is assessed only by age randomization strata for each staging category (see [Section 7.6.7](#)).

AEs are presented by system organ class and preferred term alphabetically.

### **7.7 Pharmacokinetic (PK) Analysis**

Individual subject ETV plasma concentrations are listed and plotted versus time. Mean plasma concentration vs. time profiles in original scale as well as in log scale are provided to compare pediatric subjects by age randomization strata.

Individual subject pharmacokinetic parameter values are derived by noncompartmental methods by a validated pharmacokinetic program. Concentration data are only considered valid if complete information is available on sampling time and dosing time. Additionally, pre-dose samples for semi-intensive PK are only be considered valid if they are collected prior to the dose on the day of semi-intensive PK sampling and if sampling time and dosing time information are complete. To assess the exposure of ETV in pediatric patients, summary statistics are provided for all of the pharmacokinetic parameters of ETV by age randomization strata and treatment regimen. Geometric means and coefficients of variation as well as medians, minima, and maxima are reported for Cmax, Cmin. Medians, minima, and maxima are reported for Tmax.

## **8 CONVENTIONS**

### **8.1 Missing, Unknown or Partial Dates**

Rho will provide conventions for imputing values for missing or partial dates for non-study medication start and stop dates and for AE onset dates.

### **8.2 Unknown Study Medication End Dates**

End dates of dosing that are left as 'UNKNOWN' or partial because a subject is lost to follow-up or the subject couldn't remember the exact dosing end date are assumed to be equal to the last

recorded dose start date, thus crediting the subject with 1 day of dosing. All missing dates are queried.

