# On treatment (combined with or without long-term follow-up) only.

Additional visit windows after Week 240 are defined analogously as needed.

For the on-treatment period, weeks are calculated as (measurement date - first dose date of study therapy + 1)/7. This also applies to the on-treatment and long-term follow-up periods combined.

For the ETV treatment period, weeks are calculated as (measurement date - first dose date of active ETV + 1)/7. This also applies to the ETV treatment and long-term follow-up periods combined.

For the off-treatment and long-term follow-up periods, weeks are calculated as (measurement date - last dose date of study therapy)/7.

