## 8.9 Derived Dates

Derived dates that are used commonly in analyses are defined as follows. Derivations of dose dates exclude rescue open-label ETV.

- First dose date of study therapy is the earliest start date of drug (ie, blinded therapy [ETV active or PBO] or open-label ETV) identified from valid dosing records, ie, non-missing start date and number of units per day > 0, from blinded therapy study medication CRFs. This date is used to identify treated subjects and to distinguish measurements across study periods. Note that this is also first dose date of blinded study therapy.

- Dose end date of study therapy is the latest start or end dates of drug (ie, blinded therapy [ETV active or PBO] or open-label ETV) identified from valid dosing records, ie, non-missing start or end date and number of units per day > 0 or total dose > 0. This date is used to assess time on study therapy.
- Last dose date of study therapy is the dose end date of study therapy derived only for subjects with an end of treatment subject status CRF indicating whether the subject completed the treatment period. This date is used to exclude data in antiviral activity and safety analyses, and to distinguish measurements across study periods.
- Dose end date of blinded therapy is the latest start or end date of blinded therapy (ETV active or PBO) identified from valid dosing records, ie, non-missing start or end date and number of units per day > 0, from blinded therapy study medication CRFs. This date is used to assess time on blinded study therapy.
- First dose date of open-label ETV is the earliest start date of open-label ETV identified from valid dosing records, ie, non-missing start date and total dose > 0, from open-label study medication CRFs. This date is used to distinguish measurements across blinded vs open-label treatment, and to assess time on open-label therapy.
- Dose end date of open-label ETV is the latest start or end date of open-label ETV identified from valid dosing records, ie, non-missing start or end date and total dose > 0, from open-label study medication CRFs. This date is used to assess time on open-label therapy.
- First dose date of active ETV is the first dose date of study therapy for ETV-randomized subjects, and the first dose date of open-label ETV for PBO-randomized subjects. This date is used to identify all ETV-treated subjects and to distinguish measurements across study periods.

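### Setting an unknown or partial dosing end date to the start of the last dosing record can move on-treatment data into off-treatment follow-up and start the off-treatment clock too early

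*SAP*

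**What the plan says.** SAP 8.2 covers "End dates of dosing that are left as 'UNKNOWN' or partial because a subject is lost to follow-up", and also end dates that could not be recalled. All of these are set to the last "recorded dose start date, thus crediting the subject with 1 day of dosing". The only mitigation stated is "All missing dates are queried". The rule makes no use of the known part of a partial date or of later evidence of dosing, and no sensitivity analysis is attached to it.

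SAP 8.9 builds the last dose date from these dosing records and says of it: "This date is used to exclude data in antiviral activity and safety analyses, and to distinguish measurements across study periods". Four definitions then depend on that date:

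- SAP 6.1: the on-treatment period "begins after the first day of study therapy and ends at the last dose of study therapy plus 5 days".
- SAP 6.1: off-treatment follow-up "begins on the last dose of study therapy plus 6 days and ends at the start of alternative anti-HBV therapy minus 1 day".
- SAP 8.4: values are assigned to a study period before visit windows are applied, and for follow-up, "weeks are calculated as (measurement date - last dose date of study therapy)/7".
- SAP 8.5: the EOD value is the last one up to last dose plus 5 days.

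Exposure (SAP 7.4.1 and 8.10) uses the dose end date from the same records.

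**The concern.** One day of credit looks like a cautious exposure convention, but the date does more than measure exposure. It decides which period each visit, adverse event and ALT value belongs to. If it is too early, data collected on drug are reported as post-treatment data, the EOD value comes from an earlier visit, and every off-treatment week is counted from the wrong origin. The last of these matters most for the fifth key secondary endpoint, which SAP 7.5.2.5 tests at off-treatment Week 24 with missing values counted as failures (NC = F). That test uses only children seroconverted at both Week 48 and EOD, probably a small group in which one or two reclassifications could matter.

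**Working it through.** **Inputs.** Time on therapy = (last dose − first dose + 1)/7 (SAP 7.4.1). On-treatment cut = last dose + 5 days (SAP 6.1). Off-treatment week = (measurement − last dose)/7 (SAP 8.4). Off-treatment Week 24 window = more than 18 to 30 weeks (SAP Table 8.4-1). Follow-up serology at Week 24 and every 24 weeks (Protocol Table 6.1). Treatment visits at Weeks 4, 8 and 12, then every 12 weeks (Protocol 4.1).

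**Assumption.** One dosing record opens per visit. The documents do not give record length; container assignment at each visit (Protocol 5.2) makes this plausible.

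**Step 1: the plan's own figure.** With end = start, the last record gives 0 + 1 = 1 day, as SAP 8.2 states.

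**Step 2: a partial date.** A record starts on 10 March and the end is known only as May of that year. From 10 March to 1 May is 52 days and to 31 May is 82 days. At least 52 further days are certain; the rule credits 1 day in total.

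**Step 3: the period shift.** The last record starts at Week 36 (Day 36 × 7 + 1 = 253), the true last dose is Day 336, and a sample is taken on Day 337.

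- True position: on-treatment week 337/7 = 48.1.
- Under SAP 8.2: last dose Day 253, on-treatment cut Day 258, so the sample is off-treatment at (337 − 253)/7 = Week 12.0.
- Time on therapy: 253/7 = 36.1 weeks instead of 336/7 = 48.0. The loss is 83 days (11.9 weeks).
- In a 4-week interval (record from Day 57, last dose Day 84) the loss is 27 days (3.9 weeks).

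**Step 4: the fifth key secondary endpoint.** Let L be the weeks lost. A sample at true off-treatment week w is derived as week w + L.

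- The true Week 24 sample leaves the window when 24 + L > 30, that is L > 6.
- A sample taken at the true stop is derived as week L and enters the window only when L > 18 (about 17.3 if taken 5 days after the last dose).
- For L between 6 and about 18, no scheduled serology falls in the window. Unless an unscheduled sample does, the child is missing and so a failure.

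Example: a Week 48 seroconverter finishes blinded drug at Week 96 with a record opened at Week 84. L = (672 − 589)/7 = 11.9. The true Week 24 sample is derived as week 35.9 (Week 36 window), the end-of-treatment sample as about week 12, and EOD falls back to the Week 84 value.

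If the true stop is uniform within the record, then among affected children:

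| Assumed record length | Mean loss | Maximum loss | Share with L > 6 | Share with L > 18 |
|---|---|---|---|---|
| 4 weeks | 2 | 4 | 0 | 0 |
| 12 weeks | 6 | 12 | 6/12 = 50% | 0 |
| 24 weeks | 12 | 24 | 18/24 = 75% | 6/24 = 25% |

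**Step 5: the primary endpoint.** With 82 versus 41 children and 20% versus 1%, a pooled-variance normal approximation without continuity correction gives power 0.904, matching the stated 90%. About 16 ETV responders are expected (0.20 × 82 = 16.4). Turning one into a failure gives 0.873, two gives 0.835. Such cases should be rare: children who reach Week 48 normally continue on blinded or open-label drug, which gives later dosing dates, and a child whose last record opens at the Week 48 visit keeps that sample on treatment.

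**The case against.** The strongest objections are these.

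- **The scope is narrow.** Missing dates are queried, only the last record is cut, and the last dose date exists only for children with an end-of-treatment form. A child lost with no later contact has little data to move, and that child's later dosing is unknown. This stands. Misclassification is confined to children who returned but whose date stayed unresolved. They will have later data, because children who stop drug are still followed (Protocol 4.2.3 and 5.3.2.2).
- **A reader might infer that a child still on drug will be counted as sustained at off-treatment Week 24.** With records of 12 weeks or less, an on-drug sample cannot reach the window; a loss of about 18 weeks or more is needed. The likelier error is the opposite one, a true responder counted as a failure.
- **A reader might infer that exposure-adjusted rates are biased.** This is not shown. Events and exposure are cut at the same date plus 5 days (SAP 6.1 and 8.10), so numerator and denominator shrink together, and no direction follows.
- **Some summaries are insensitive to the cut.** Deaths are reported regardless of period, while disease progression, malignancies and growth combine treatment and long-term follow-up. This stands.
- **Under-crediting is conservative for the 48-week exposure requirement.** That is true for exposure. It does not justify labelling on-drug events and serology as off-treatment.

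**Conclusion.** The point holds, within limits. For a partial date the rule can give an end date that the child's own record contradicts. For children with an end-of-treatment form and an unresolved date, that can move visits, adverse events and ALT flares off treatment, change the EOD value, understate exposure and start the off-treatment clock too early. Under the one-record-per-visit assumption the loss is at most 27 days in a 4-week interval and 83 days in a 12-week interval; longer records would lose more. For the fifth key secondary endpoint, a loss above 6 weeks probably turns a sustained responder into an NC = F failure, assuming follow-up visits are timed from the true stop. The documents give neither the number of affected children nor the record length, so the total effect cannot be sized. They do not support a claim that the primary result is at risk.

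**What to change.** Amend SAP 8.2 as follows.

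- **Partial date:** impute within the known month or year, no earlier than the last record's start and no later than the earliest of the end-of-treatment form date, last contact and the start of alternative anti-HBV therapy. State in advance which day of the allowed interval is used.
- **Fully unknown date:** use the latest date in the database with documented dosing, if there is one, under the same bounds. Otherwise keep the current rule.
- **Sensitivity analysis:** report the current rule for the fifth key secondary endpoint and for the on- and off-treatment adverse event and ALT-flare summaries.

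The cost is SAP wording, one changed derivation and a repeat of those tables. Last contact and the start of alternative therapy are already derived in SAP 8.9, and the end-of-treatment form already feeds the last dose date. Dispensing and return dates are required only in source documents (Protocol 5.6), so whether the database holds them must be checked. The downside is that exposure may be over-credited by up to the width of the known interval, about a month when the month is known. That could move some post-treatment events on treatment, which the sensitivity analysis would help to show.
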